4.2 Inclusion Criteria

4.2.1 Inclusion Criteria

Participants must meet all of the following criteria to be eligible for randomization as study participants.

1. Aged ≥ 18 and ≤ 60 years at the time of informed consent.
2. Meets EULAR/ACR 2019 criteria for SLE [3].
3. Moderately severe, active, but non-organ threatening disease. Specifically, signs or symptoms meeting criteria for a minimum of:
 - a. 1 BILAG A (severe) score in the constitutional, musculoskeletal or mucocutaneous system at the time of screening. See Section 4.3, *Exclusion Criteria* number 2 for additional detail.
 - b. 2 BILAG B (moderate) activity scores in any organ systems; or
 - c. 1 BILAG B (moderate) activity score in any organ systems **and** a SELENA-SLEDAI score of ≥ 6 .
 - If there is only 1 BILAG B score:
 - If a musculoskeletal BILAG B is scored due to moderate arthritis, where some loss off functional range of movements was present on several days over the last 4 weeks, there must also be a minimum of at least 3 joints that are both tender and

swollen due to lupus disease activity in wrists, MCPs or PIPs for the participant to qualify.

- If a mucocutaneous BILAG B is scored due to acute or subacute cutaneous skin eruption, the rash must cover at least 4% of the body surface area for the participant to qualify. Any active discoid lesion or other form of chronic cutaneous lupus would be qualifying.

4. Approval, by an adjudication committee of a brief entry packet describing the type, severity and duration of symptoms meeting the minimal criteria for entry. The participant will meet this criterion if the committee is confident of all of the following:
 - a. Convincing diagnosis of SLE,
 - b. Active disease, due to SLE, warranting the potential of dual therapy with potent immune modulators,
 - c. No medical or other condition to contraindicate participation in a placebo-controlled, outpatient study of this design.
5. Women of childbearing potential must have a negative serum pregnancy test at screening.
6. Able or willing to use reliable methods of contraception, as outlined in the Mycophenolate REMS brochure for health care providers, from 4 weeks prior to first randomization to 6 weeks after completion of the study. This criterion applies to females of reproductive potential. Mycophenolate REMS Program acceptable contraceptive methods are outlined in Appendix 1, see Section 19.1.

4.2.2 Inclusion Criteria Required Prior to Randomization

Participants who meet the following criterion at the Stage 2 Randomization Visit may proceed to randomization in Stage 2:

7. After completion of corticosteroid injection(s) and prior to randomization in Stage 2, the participant and his/her physician must agree that disease activity has improved sufficiently from screening such that randomization is acceptable.
 - a. The physician must score the CGI-C [4] as “moderately better” or “much better” prior to randomization.
 - The reference value for the CGI-C should be the investigator’s determination of the participant’s condition at the Screening Visit.
 - b. The participant must agree that his/her symptoms have improved (yes/no).

4.3 Exclusion Criteria

Participants who meet any of the following criteria are not eligible for randomization as study participants:

1. Inability or unwillingness of a participant to understand and provide written informed consent or comply with the study protocol.
2. BILAG A (severe) disease in the Cardiorespiratory, Neuropsychiatric, Gastrointestinal, Ophthalmic, Renal, or Hematological Systems.
3. Severe or unstable nephritis defined as any of the following:
 - a. History of confirmed Class 3-5 nephritis within the last 2 years,

- b. History of confirmed Class 3-5 nephritis > 2 years ago in the absence of documented treatment including both induction and maintenance therapy,
- c. UPCR > 1 g/g at screening,
 - If UPCR is > 0.5 g/g and ≤ 1 g/g at screening, then a second assessment must be completed with at least 1 week between assessments. If the second assessment is > 1 g/g or has increased by ≥ 0.3 g/g, then the participant is excluded.

4. Evidence of chronic kidney disease defined as eGFR < 45 mL/min per 1.73 m² at screening, where $175 \times (\text{Creatinine}/88.4) - 1.154 \times (\text{Age}) - 0.203 \times (0.742 \text{ if female}) \times (1.212 \text{ if of African descent})$ [5].

5. History of cirrhosis or chronic liver disease unrelated to SLE other than fatty liver disease.

6. History, within 1 year of the Screening Visit, of uncontrolled SLE that would have warranted a BILAG A (except mucocutaneous, constitutional, musculoskeletal) including, but not limited to, hemolytic anemia, neuropsychiatric lupus, or interstitial lung disease.

7. Uncontrolled HTN at the Screening or Randomization Visits defined as a blood pressure > 150/100 with or without treatment, not to exceed 3 complementary antihypertensive treatments.

8. Any of the following laboratory values during screening:

- a. Hemoglobin (Hg) < 8.0 g/dL,
- b. WBC < 2.0 × 10⁹ cells/L,
- c. ANC < 1.0 × 10⁹ cells/L,
- d. Platelets < 60 × 10⁹ cells/L at screening,
 - If platelets < 70 × 10⁹ cells/L at screening, platelet count should be retested 2 weeks later. If platelets are < 60 × 10⁹ cells/L at retest, participant will be excluded
- e. AST or ALT > 2.5 times the ULN,
- f. Serum IgG levels < 5 g/L

9. Use of ≥ 40 mg/day of prednisone within 4 weeks prior to the Screening Visit or use of > 20 mg/day of prednisone at screening.

10. Unwilling or unable to taper to ≤ 10 mg/day of prednisone or equivalent by the day of randomization.

11. Use of hydroxychloroquine, chloroquine, or quinacrine, if taking, at a prescribed dose that has not been stable for at least 2 months prior to randomization.

12. Use of MMF within 1 year of randomization.

13. Use of CNIs within 3 months of randomization. Topical formulations applied stably for at least one month are allowed.

14. Use of rituximab, obinutuzumab, ocrelizumab, or long-acting B cell depletion agents within 1 year of randomization. Use of agents ≥ 6 months and within 1 year of randomization is permitted if there is evidence of B cell reconstitution as defined as CD19+ counts of ≥ 50 cells/µL.

15. History of intolerance or allergy to MMF, voclosporin, or long-acting corticosteroid preparations.
16. Individuals with known hypersensitivity to Polysorbate 80 (Tween).
17. A woman who is pregnant, breastfeeding, or planning pregnancy from the time of consent until 6 weeks after completion of the study.
18. Any participant with plans for major surgery during the time of the trial.
19. Active infections requiring hospitalization or intravenous antibiotics within 1 month prior to the Screening Visit.
20. Any grade 2 infection or higher from 14 days prior to the Screening Visit and through the screening period that has not resolved by randomization.
21. Acute herpes zoster within 4 months of the Screening Visit.
22. Positive results from a SARS-CoV-2 antigen test administered 2 days prior to and on the day of first randomization.
23. Positive Quantiferon Gold (or equivalent) assay. Indeterminate Quantiferon Gold (or equivalent) assays must be repeated (with same or other interferon gamma release assay per local policy) and shown to be negative. Alternatively, if the Quantiferon Gold (or equivalent) assay remains indeterminate, a participant must have a negative PPD. Finally, if the participant has had the BCG vaccine or has some other condition complicating the interpretation of TB testing, consultation with infection disease specialist must be obtained.
 - Participants diagnosed with latent TB are eligible but must have received appropriate prophylaxis for 30 days prior to initiation of Stage 2 treatment.
24. Serologic evidence at screening of chronic infections including:
 - a. HIV infection.
 - b. Hepatitis B as indicated by surface antigen or hepatitis B core antibody positivity; if a participant has an isolated positive hepatitis B core antibody, they will be eligible to participate in the study if they are negative for reflex viral load at Screening.
 - c. Hepatitis C as indicated by anti-hepatitis C antibody positivity; if a participant is Hepatitis C antibody positive, they will be eligible to participate in the study if they are negative for viral load at Screening.
25. Current, diagnosed, or self-reported drug or alcohol abuse within the last 6 months that, in the opinion of the investigator, would interfere with the ability to comply with study protocol.
26. Recipient of live attenuated vaccine(s) within 8 weeks of the Screening Visit.
27. Use of investigational drugs (excluding SARS-CoV-2 vaccinations or SARS-CoV2 therapeutics) within 8 weeks of the Screening Visit or 5 half-lives, whichever is longer.
28. Past or current mental or physical problems or findings from physical examination or laboratory testing that are not listed above, which, in the opinion of the investigator, may pose additional risks from participation in

the study, may interfere with the participant's ability to comply with study requirements, or may impact the quality or interpretation of the data obtained from the study.

5 Known and Potential Risks and Benefits to Participants

5.1 Risks of MMF as cited in the USPI

Risks cited below are noted in the United States Prescribing Information (USPI) for MMF updated 2/2019 [28].

Contraindications: MMF is contraindicated in patients with a hypersensitivity to MMF, MPA, any component of the drug product, and in patients who are allergic to Polysorbate 80 (Tween).

Embryofetal Toxicity: MMF use has been associated with risk of first trimester pregnancy loss and congenital malformations, especially external ear and other facial abnormalities including cleft lip and palate, and, according to the package insert, anomalies of the distal limbs, heart, esophagus, kidney and nervous system. Embryofetal Toxicity is listed as a boxed warning in the package insert [28].

Lymphoma and Other Malignancies: Patients receiving MMF, or immunosuppressants in general, are at increased risk of developing lymphomas and other malignancies, particularly of the skin. The risk appears to be related to the intensity and duration of immunosuppression rather than to the use of any specific agent. Malignancies are listed as a boxed warning in the package insert [28].

Post-transplant lymphoproliferative disorder (PTLD) developed in 0.4% to 1% of patients receiving MMF (2 g or 3 g) with other immunosuppressive agents in controlled clinical trials of kidney, heart and liver transplant patients. The majority of PTLD cases appear to be related to Epstein Barr Virus (EBV) infection. The risk of PTLD appears greatest in those individuals who are EBV seronegative, a population which includes many young children.

Infections: Patients receiving MMF, or immunosuppressants in general, are at increased risk of developing bacterial, fungal, protozoal and new or reactivated viral infections, including opportunistic infections. The risk increases with the total immunosuppressive load. These infections may lead to serious outcomes, including hospitalizations and death. Serious viral infections reported include: Polyomavirus-associated nephropathy, especially due to BK virus infection; JC virus-associated progressive multifocal leukoencephalopathy Cytomegalovirus (CMV) infections, especially for CMV seronegative transplant patients who receive an organ from a CMV seropositive donor; and viral reactivation in patients infected with Hepatitis B and C. Serious infections are listed as a boxed warning in the package insert [28].

Blood Dyscrasias: Neutropenia and Pure Red Cell Aplasia (PRCA): Severe neutropenia [$ANC < 0.5 \times 10^3/\mu L$] developed in transplant patients receiving MMF 3 g daily, a dose higher than intended for this study. Neutropenia has been observed most frequently in the period from 31 to 180 days post-transplant in patients treated for prevention of kidney, heart and liver rejection.

Cases of PRCA have been reported in patients treated with MMF in combination with other immunosuppressive agents.

GI Disturbances: Diarrhea and vomiting are common. Gastrointestinal bleeding requiring hospitalization, ulceration and perforations were observed in clinical trials.

5.2 Risks of voclosporin as cited in the Investigator Brochure and Package Insert

Risks cited below are noted in the voclosporin Investigator's Brochure [65] and Package Insert [21].

Contraindications:

- Voclosporin is contraindicated in patients with hypersensitivity or anaphylactic reactions to voclosporin or any constituents [65].
- Voclosporin should not be given with strong CYP3A4 inhibitors (e.g., ketoconazole, itraconazole, clarithromycin). Voclosporin exposure was 18-fold higher in the presence of the strong CYP3A4 inhibitor (ketoconazole) compared to voclosporin administered alone [65].
- Voclosporin should not be given in patients with hypertensive urgency or BP > 165/105 mmHg [21].
- Voclosporin is not recommended for patients with a baseline eGFR < 45 mL/min per 1.73 m² unless benefit exceeds risks [21].

Hypertension: Voclosporin can cause or worsen systemic HTN. Mild or moderate HTN is encountered more frequently than severe HTN. Serious adverse drug reactions (SADR) classified by the MedDRA preferred term "hypertension" are considered "expected" for the purpose of regulatory reporting. Life-threatening or fatal SADRs are "unexpected". HTN may require antihypertensive therapy.

Decreases in GFR: Voclosporin can cause chronic and/or acute nephrotoxicity. eGFR should be monitored regularly and dose adjustments considered for decreases in eGFR. In the first 4 weeks of treatment with voclosporin, hemodynamic reductions in eGFR have been observed, which subsequently stabilize. Chronic nephrotoxicity has been observed at levels of CNI suppression needed in organ transplantation. The level of CNI suppression of voclosporin in LN is lower than that generally required in transplantation induction and maintenance. Renal impairment and acute kidney injury occurred more frequently in voclosporin-treated patients than placebo-treated patients.

Serious Infections: Immunosuppressants, including voclosporin, may increase the risk of developing bacterial, viral, fungal, and protozoal infections, including opportunistic infections. These infections may be serious and have fatal outcomes. Serious infections are listed as a boxed warning in the package insert [21].

Neurotoxicity: Voclosporin, like other CNIs, may cause a spectrum of neurotoxicities, the most severe of which are posterior reversible encephalopathy syndrome (PRES), delirium, seizure, and coma; others include tremors, paresthesias, headache, mental status changes, and changes in motor and sensory functions.

Hyperkalemia: Voclosporin has been reported to cause hyperkalemia which may be exacerbated by use of other agents such as potassium-sparing diuretics, ACE inhibitors and angiotensin receptor blockers.

QTc prolongation: Voclosporin prolongs the QTc interval in a dose-dependent manner after single dose administration at a dose higher than the recommended LN therapeutic dose. The use of voclosporin in combination with other drugs that are known to prolong QTc may result in clinically significant QT prolongation.

Pure Red Cell Aplasia: Although not reported with voclosporin, cases of PRCA have been reported in patients treated with other CNIs.

Lymphomas and Other Malignancies: Voclosporin is an immunosuppressant. Long-term treatment with immunosuppressants increases the risk of developing lymphomas and other malignancies, particularly of the skin. The

risk appears to be related to the intensity and duration of immunosuppression rather than to specific use of a medication. Patients should be advised to avoid or limit unprotected exposure to sunlight and UV light. Malignancy is a boxed warning in the package insert [21].

Other Concerns:

- Voclosporin should be avoided during pregnancy because of the alcohol content of the drug formulation. Nonclinical studies with oral voclosporin showed that low levels of voclosporin crossed the placental barrier. The available data on the use of voclosporin in pregnant women are insufficient to determine whether there is a drug-associated risk for major birth defects, miscarriage, or adverse maternal or fetal outcomes. Study product will be discontinued in any participant who becomes pregnant, and the pregnancy will be followed per Section 12.6, *Pregnancy Reporting*.
- Limited transfer to breast milk was also demonstrated in rats. No information is available on the presence of voclosporin in human milk, the effects of voclosporin on the breastfed infant, or the effects of voclosporin on milk production.

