- If the participant is deemed a Stage 2 treatment failure as defined in protocol Section 3.2, *Primary Endpoint*, and a corticosteroid injection is deemed insufficient and a new or increased lupus medication is required, then a blood sample for mechanistic studies will be drawn, Stage 2 study-provided medication will be stopped, and the new or increased lupus medication will be started outside of the study. The participant will not be eligible for Stage 3 but will be followed to Stage 2 Week 24 or 4 weeks \pm 10 days after the last dose of study-provided medication, whichever is later, before exiting the study. Participants who exit the study at Stage 2 Week 24 should complete all End of Study/Safety Follow-Up visit assessments at this time.

Participants who have not failed Stage 2 on or before the Stage 2 Week 24 visit will continue on Stage 2 study-provided medication through Stage 2 Week 48 or until treatment failure, whichever occurs first.

- If the participant is deemed a Stage 2 treatment failure after Stage 2 Week 24, then study-provided medication will be stopped. Prior to treatment with a corticosteroid injection or a new or increased lupus medication outside of the study, a blood sample for mechanistic studies will be drawn. The participant will return for an End of Study/Safety Follow-Up Visit 4 weeks \pm 10 days after the final dose of study-provided medication.
- Participants who have not failed Stage 2 on or before the Stage 2 Week 48 visit will return for an End of Study/Safety Follow-Up Visit 4 weeks \pm 10 days after the final dose of study-provided medication.

Severe lupus manifestations that are life-threatening or organ-threatening should prompt consideration for withdrawal from the study in order to enable maximal therapy with corticosteroids and other lupus medications. The ultimate decision on withdrawal should be left up to the clinical judgment of the investigator.

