6.1.2.2 Dosage, Preparation, and Administration

Voclosporin will be provided in 7.9 mg gel capsules for oral administration. Placebo for Voclosporin will be provided as gel capsules for oral administration.

The rate and extent of voclosporin absorption is decreased on co-administration with food, therefore, to maximize absorption it is recommended that voclosporin is administered on an empty stomach.

Voclosporin should be stored at 20° to 25°C (68° to 77°F).

Stage 3 Dosing:

- **Weeks 1-24:** 23.7 mg Voclosporin/Placebo (3 x 7.9 capsules) twice daily

Voclosporin/Placebo dose may be modified for renal impairment, see Section 6.4.7, *Decreases in eGFR*.

- Allowed voclosporin/placebo dose reductions include: 15.8 mg or Placebo (2 capsules) orally twice daily and 7.9 mg or Placebo (1 capsule) orally twice daily.

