Eligible and consenting participants who have a qualifying Stage 2 treatment failure at or before the Stage 2 Week 24 Visit will immediately proceed with Stage 3 re-randomization according to Table 8.2, *Stage 3 Schedule of Events*. If a qualifying Stage 2 treatment failure is identified after a visit has taken place due to laboratory values, the participant should return for Stage 3 re-randomization within 5 days of discovery of the event. See Section 8.2 *Study Procedures and Assessments* for more information on individual clinical and research assessments.

8.1.5 Study-Provided Medication for Stage 3

- Stage 3 study-provided medication (MMF/voclosporin or MMF/Corresponding placebo for voclosporin) is dispensed to eligible participants at the Stage 3 Re-Randomization Visit. Dosing begins on the day after re-randomization.
- Study medication compliance is evaluated at all following visits.
- Refer to Section 3.1.3, *Stage 3 Re-Randomization* for additional information.

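### Stage 3 can start voclosporin without any blood pressure or eGFR condition, although Section 5.2 gives limits for both

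*Combined protocol and SAP*

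**What the plan says.** Section 5.2 lists two relevant limits under its contraindications for voclosporin: "Voclosporin should not be given in patients with hypertensive urgency or BP > 165/105 mmHg", and "Voclosporin is not recommended for patients with a baseline eGFR < 45 mL/min per 1.73 m² unless benefit exceeds risks".

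The protocol's own eligibility limits come earlier. Exclusion 4 in Section 4.3 is "Evidence of chronic kidney disease defined as eGFR < 45 mL/min per 1.73 m² at screening". Exclusion 7 is "Uncontrolled HTN at the Screening or Randomization Visits defined as a blood pressure > 150/100".

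Entry to Stage 3 is governed by 3.1.2 and 8.1.4. Under 8.1.4, "Eligible and consenting participants who have a qualifying Stage 2 treatment failure at or before the Stage 2 Week 24 Visit will immediately proceed" to re-randomization. Under 3.1.2 the failure qualifies if a steroid injection is judged enough and no new or increased lupus drug is needed. For failures that do need other treatment, 3.1.2 says "The participant will not be eligible for Stage 3 but will be followed to Stage 2 Week 24" or longer. Section 8.1.5 adds: "Dosing begins on the day after re-randomization". Section 7.3.4 bars strong CYP3A4/5 inhibitors and inducers in Stage 3.

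The voclosporin or placebo dose starts at 23.7 mg twice daily for everyone. On kidney function, 6.1.2.2 says "Voclosporin/Placebo dose may be modified for renal impairment, see Section 6.4.7".

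**The concern.** Section 8.1.4 uses the word eligible, but no list of Stage 3 criteria defines it, and none of the stated conditions concerns blood pressure or eGFR. Followed as written, the protocol allows a participant to start blinded voclosporin at a blood pressure at which 5.2 says it should not be given. It also allows a start at an eGFR for which 5.2 calls for a benefit-risk judgement that no Stage 3 step records.

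Changes between the last check and entry are plausible. Section 6.4.7 notes clinically significant eGFR decreases on MMF alone as well as on the combination, and about 36 of the expected entrants come from the Stage 2 MMF arm. A steroid injection may be given at the failure visit, and 5.3 asks for hypertension monitoring with such injections. The combined safety data in 1.5.2.3 show more GFR decrease (29% against 11%) and more hypertension (21% against 11%) on voclosporin than on placebo.

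The omission looks unintended, because another contraindication from 5.2, strong CYP3A4 inhibitors, was carried into Stage 3 by 7.3.4. What is at stake is participant safety and the renal safety data of Stage 3, not the Stage 2 primary comparison.

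**Working it through.** The plan states no figure to reproduce here. The check sets the text of each section side by side, with simple arithmetic on timing, head count and the eGFR dose rule.

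**1. Where each limit is applied**

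| | Limit in 5.2 | Last eligibility check | Condition at Stage 3 entry |
|---|---|---|---|
| Blood pressure | > 165/105 or hypertensive urgency | Stage 2 randomization (> 150/100 excluded) | none |
| eGFR | < 45 unless benefit exceeds risks | screening (< 45 excluded) | none |

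Exclusion 7 is read as covering the Stage 2 visit only, because the protocol consistently calls the Stage 3 visit re-randomization.

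**2. Age of the last check at Stage 3 entry**

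- eGFR: up to 4 weeks of Stage 1 + 24 weeks of Stage 2 = 28 weeks.
- Blood pressure: 24 weeks.
- Windows: 5 days on the Week 24 visit + 5 days for re-randomization (Table 8.2, footnote N) = up to 10 days more.

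Both are measured every 4 weeks in between and at the failure visit, but no rule uses the values to decide entry. Chemistry is a central-laboratory test, drawn after the physician has assessed failure (8.2.2; Table 8.1, footnote B). Re-randomization may take place that same day, with dosing the next day. As far as the extracted Table 8.2 can be read, no vital signs or chemistry are scheduled at re-randomization; the first are at Week 2.

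**3. Number exposed (Section 13.7)**

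- From placebo: 0.80 × 60 = 48. From MMF: 0.60 × 60 = 36. Total 84.
- Allocation 1:1: 84 / 2 = 42 on voclosporin.

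**4. What the 6.4.7 dose rule does at different entry values**

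When eGFR is below 60, 6.4.7 cuts the dose at a fall of 20–30% from the Stage 3 baseline and withholds at a fall above 30%. For baseline B, the first cut comes at 0.8 × B and withholding below 0.7 × B. The renal safety endpoint in 3.3.2 is Grade 3 or higher chronic kidney disease with eGFR < 30.

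| Entry eGFR (illustrative) | First cut | Withhold below | Relation to 30 |
|---|---|---|---|
| 45 | 0.8 × 45 = 36 | 0.7 × 45 = 31.5 | both steps come first |
| 40 | 0.8 × 40 = 32 | 0.7 × 40 = 28 | below 30 before withholding |

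The boundaries follow from setting each step equal to 30:

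- First cut: 30 / 0.8 = 37.5.
- Withholding: 30 / 0.7 = 42.9.

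For entry below 37.5, eGFR is under 30 before any dose step applies. For entry from 37.5 to about 42.9, it falls under 30 after the first cut but before withholding. At the 45 limit, both steps come before 30.

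**The case against.** The strongest reply is that other controls exist.

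- **Blood pressure management.** Section 6.4.6 applies throughout the study and directs antihypertensive treatment of concerning values. Any reading above 165/105 is Grade 3 by the definition in 3.3.2 (at least 160 systolic or 100 diastolic), so a related event can lead to holding and then stopping study drug.
- **Discretion.** Sections 6.5 and 11.2 let the physician, investigator or medical monitor stop treatment or participation.
- **Diversion.** Failures needing new lupus treatment, as a renal flare often would, do not enter Stage 3.
- **Conditional eGFR limit.** Section 5.2 allows a benefit-risk judgement, and the adjudication committee considers suitability for dual therapy at study entry.
- **Missing material.** Figure 1 is not available, and Table 8.2 is broken in extraction.

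These points reduce the likely number affected but do not close the gap. Section 6.4.6 sets no threshold for starting Stage 3 drug. General discretion does not require anyone to look at blood pressure or eGFR before re-randomization. The injection condition tests lupus severity, not blood pressure or kidney function. The committee's judgement is made before Stage 2.

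Three qualifications stand. The eGFR limit is not an outright prohibition. The endpoint is Grade 3 or higher chronic kidney disease with eGFR < 30, so one reading below 30 need not be an endpoint event. That the 45 limit keeps the dose steps ahead of 30 follows from the arithmetic; the protocol does not give it as a purpose.

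**Conclusion.** The concern holds, with high confidence on the readable text. The protocol can start a participant on voclosporin outside limits that it states itself. How many would be affected cannot be derived from the documents, and the number is probably small; the population at issue is about 84 entrants, about 42 on active drug. The eGFR entry values of 40, 37.5 and 42.9 illustrate how the dose rule behaves and are not predictions. The conclusion assumes that exclusion 7 does not reach the re-randomization visit and that Figure 1 contains no additional entry condition. Stage 3 is exploratory and the Stage 2 primary analysis is unaffected. This is a safety gap that should be closed, not a flaw in the main inference.

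**What to change.** Add to 8.1.4, with a cross-reference in 3.1.2, two conditions to be met before re-randomization:

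- Blood pressure at the failure or re-randomization visit is no higher than 165/105 (or the trial's own, stricter 150/100), with no hypertensive urgency. A high value may be treated and rechecked within the existing 5-day window.
- The eGFR result from the failure visit has been reviewed and is at least 45, or a benefit-risk decision agreed with the medical monitor is on file.

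Participants who do not meet these should follow the 3.1.2 path for failures not eligible for Stage 3. That path is worded for people who need new lupus medication, so a sentence extending it is needed. Applying the conditions to everyone before re-randomization preserves the blind and avoids exclusions after randomization.

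The cost is a short amendment. Vital signs and chemistry are already collected at the failure visit, so no new test is needed beyond an occasional repeat blood pressure reading. Some participants would wait for a laboratory result; this assumes that the central result returns within 5 days, and the documents give no turnaround time. A few may not enter Stage 3, slightly reducing the planned 84.
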